## 8.1 **Primary study parameter(s)**

The primary analysis is aimed at comparing the effects of MBCT + TAU on depressive symptoms. The primary outcome parameter will be the total scores on the IDS-C. In order to investigate consolidation of treatment effect, we will follow-up participants for another 15 months. We will use a multilevel regression model for repeated measures to analyse differences between baseline, 3 months, 6 months, 9 months, 12 months, and 15 months follow-up measurements.

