## 4.4 Sample size calculation

Sample size calculation is based on the estimated change in depressive symptoms form pre- to posttreatment. As we aim to include patients with all levels of depressive symptoms, we based our calculation on a previous study conducted at the Radboudumc Centre for Mindfulness (van Aalderen et al., 2012). In this study, levels of depression as assessed with the Inventory of depressive symptomatology – self-rated (IDS-SR) decreased in the MBCT+TAU group (n = 102) from 14.9 ( $\pm$  9.2) to 10.3 ( $\pm$  7.8) whereas the TAU group (n = 103) showed no change in depression levels (pretreatment: M = 16.2 ( $\pm$  9.4) and posttreatment: M = 16.2 ( $\pm$  9.8). This corresponded to an effect size of 0.5 for reduction of depressive symptoms in patients with recurrent (unipolar) depression (remitted n = 124, currently depressed n = 58). Based on a two-sided test with an alpha of 0.05 and a power of 80%, with an estimated effect size of 0.5, including a design factor of 1 – r2 (0.75), and taking account of a conservative estimate of 40% loss to follow-up, we intend to recruit N = 160 patients (80 per group).

We anticipate that about 25% of the population will have to be excluded due to (hypo)manic symptoms (when exceeding the maximum on the Young Mania Rating Scale) or other exclusion criteria. We further expect about 25% of the eligible patients to be interested in the study.

Approximately 690 BD patients are treated in ProPersona, with 518 (75%) meeting the inclusion criteria, of whom 130 (25%) would probably be interested to participate. The intended number of participants (n = 60) falls comfortably within this estimate. The number of BD patients treated in Dimence is about 900, with 675 (75%) meeting the inclusion criteria, of whom 169 (25%) would probably be interested to participate. Again, the intended number of participants (n = 50) falls well within this estimate. Approximately 650 BD patient are treated in Altrecht, with 100-150 new patients per year. About 487 (75%) of BD patients would be meeting the inclusion criteria, of whom 122 (25%) would probably be interested. The intended number of participants (n = 50) therefore seems feasible. Moreover, we will recruit patients through the patient association Vereniging voor Manisch Depressieven en Betrokkenen (VMDB) and the psychiatry department of the Canisius Wilhelmina

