#### 6.1.1 Main study parameter/endpoint

The primary endpoint of the study is severity of depressive symptoms at 3 months follow-up (T1), assessed with the *Inventory of Depressive Symptomatology – Clinician administered* (IDS-C; Akkerhuis, 1997). The IDS-C has good psychometric qualities (Rush, Gullion, Basco, Jarrett, & Trivedi, 1996; Trivedi et al., 2004) and will be administered by trained research assistants.

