## 6.6 Follow-up of subjects withdrawn from treatment

Dropouts will be contacted by phone and asked to fill out the remaining questionnaires to supply the researchers with a post measurement and follow-up. Dropouts will be reminded that they are free to refuse.

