# 8. STATISTICAL ANALYSIS

Multilevel analysis will be used to account for the cluster-randomized design and therefore the hierarchical structure of the data, with outcome variables at the pre- and postmeasurements at the lowest level, nested within individuals, nested within treatment groups (for the intervention condition), and nested within condition (MCBT + TAU vs TAU). Any baseline parameters that may be inadvertently unequally distributed between the conditions are included as covariates. Multilevel logistic regression will be performed for dichotomous outcomes and multilevel regression analysis for normally distributed continuous outcomes. The clinical outcome data will be analysed and reported according to the CONSORT guidelines, i.e. on intention-to-treat basis. Given the anticipated drop-out, we will also analyze and report on the per-protocol group, and discuss possible differences between the two analysis sets.

Additional analyses will be performed within subgroups with and without a current depressive episode. To account for possible differences between therapy groups, we will add a random group effect. Sensitivity analyses will be conducted with different scenarios of imputed data sets, in case of missing data, to examine the influence of missing data on the pattern of outcomes.

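### The sample size presumes a T1 comparison adjusted for baseline IDS-C, but sections 8 and 8.1 fix neither that adjustment nor T1 as the tested contrast

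*Protocol*

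**What the plan says.** - **Protocol 4.4, Sample size calculation.** "Sample size calculation is based on the estimated change in depressive symptoms" from before to after treatment, with effect size 0.5, two-sided alpha 0.05 and 80% power, "including a design factor of 1 – r2 (0.75), and taking account of a conservative estimate of 40% loss to follow-up". The result is 80 per group, 160 in total.
- **Protocol 6.1.1, Main study parameter/endpoint.** "The primary endpoint of the study is severity of depressive symptoms at 3 months follow-up (T1"), measured with the IDS-C. The Summary says the same.
- **Protocol 8, Statistical analysis.** A multilevel model "with outcome variables at the pre- and postmeasurements at the lowest level, nested within individuals". On covariates: "Any baseline parameters that may be inadvertently unequally distributed between the conditions are included as covariates".
- **Protocol 8.1, Primary study parameter(s).** The outcome is the IDS-C total score, with no time point attached, analysed in a "multilevel regression model for repeated measures to analyse differences between baseline, 3 months, 6 months, 9 months, 12 months, and 15 months follow-up measurements". Section 8.2 uses the same model description for the secondary outcomes.

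**The concern.** A 1 - r² factor may be counted in a sample size only if the analysis conditions on the baseline score in every case. The analysis text does not commit to that. Baseline IDS-C appears among the outcomes, no constraint on the baseline means is stated, and the one covariate rule given depends on what the data show, with no threshold. The T1 contrast, which is what 4.4 and 6.1.1 are about, is not picked out from the comparisons among six time points.

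At stake is whether the primary test has the precision that 4.4 relies on. A second issue is that the form of that test could be settled after the baseline data are seen.

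**Working it through.** **Inputs.** From 4.4: d = 0.5, two-sided alpha 0.05, power 80%, factor 0.75, loss 40%, 80 per arm. The factor implies r = 0.5; r itself is neither stated nor sourced.

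**1. Reproducing N.**
- The two-sample t-test needs 63.77 per arm.
- 63.77 × 0.75 = 47.8, so 48 with T1 data.
- 47.8 / 0.6 = 79.7, so 80 per arm and 160 in total. The stated figure is reproduced.
- Without the factor, the t-test number rounded up is 64, and 64 / 0.6 = 106.7, so 107 per arm and 214 in total (63 / 0.6 = 105 per arm, 210 in total, with the normal approximation).
- Other readings of 0.75 fail. Taken as r² it gives 27 per arm, and taken as r it gives 47. It is therefore the baseline-adjustment multiplier.

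**2. Where the 0.5 comes from.** In the cited earlier trial, change was 14.9 - 10.3 = 4.6 with MBCT and 16.2 - 16.2 = 0 with TAU. The pooled baseline SD is √((9.2² + 9.4²)/2) = 9.3, and 4.6 / 9.3 = 0.49. So 0.5 can be read as a difference in change, which makes a change contrast one plausible reading of the plan.

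**3. Variance of the T1 contrast per arm** (SD 1, 80 baselines, n₁ patients with T1 data):
- Baseline as covariate, or baseline means constrained equal: (1 - r²)/n₁.
- Baseline as outcome with free means, change contrast: (1 - r²)/n₁ + (1 - r)²/80.

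At r = 0.5 and n₁ = 48 these are 0.75/48 = 0.01563 and 0.01563 + 0.25/80 = 0.01875. The standard errors of the difference are √(2 × 0.01563) = 0.177 and √(2 × 0.01875) = 0.194.

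**4. Power at d = 0.5** (t / normal approximation):

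| r | Loss at T1 | n₁ | Adjusted | Free baseline |
|---|---|---|---|---|
| 0.5 | 40% | 48 | 79.9 / 80.7% | 72.4 / 73.3% |
| 0.5 | 30% | 56 | 85.7 / 86.3% | 77.8 / 78.6% |
| 0.5 | 25% | 60 | 88.0 / 88.5% | 80.1 / 80.7% |
| 0.5 | 20% | 64 | 90.0 / 90.4% | 82.1 / 82.7% |
| 0.4 | 40% | 48 | 75.3 / 76.2% | 65.5 / 66.4% |
| 0.6 | 40% | 48 | 85.8 / 86.5% | 80.7 / 81.5% |

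A change score in completers only, with variance 2(1 - r)/48, gives 67.9 / 68.8% at r = 0.5. The multilevel model does better because it keeps all 80 baselines.

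**5. If the imbalance rule did apply to baseline IDS-C.** This is an assumption, as are the thresholds. Simulation at r = 0.5 and n₁ = 48 (40,000 replicates, no stratification) gave 79.4% power when always adjusted and 71.9% when never adjusted. Adjusting only when imbalance was seen gave 72.6% (p < 0.05), 73.2% (p < 0.10) and 73.3% (standardised difference above 0.25). Type I error was 0.041-0.049 throughout.

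None of these figures allows for clustering by therapy group, and neither does 4.4. With an assumed ICC of 0.01-0.05 in the MBCT arm and six members per group with T1 data, adjusted power is 79.5-74.5% and free-baseline power 72.1-67.7%. Both fall, and the gap stays at about 7 points.

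**The case against.** The strongest reply is that the sections are compatible. How baseline enters a mixed model is often left to the SAP. The 1 - r² factor is itself a sign that baseline IDS-C is meant to be used. T1 is already the primary endpoint in 6.1.1 and the Summary, and 8.1 describes the longer follow-up as a check on consolidation of effect. Much of this stands: the intended endpoint is identifiable, and nothing in 8 forbids adjustment. What remains is that the protocol does state a covariate rule and a model, and neither delivers what its own sample size counts on.

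Three stronger readings are tempting, and the documents do not support them.

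- *Section 8 adjusts only for imbalanced variables.* It says that such variables are included, not that others are excluded. The list headed Baseline parameters in 6.1.3 does not contain IDS-C, so the rule may not concern it. The simulation in step 5 is therefore illustrative.
- *The trial is underpowered, or N = 160 is wrong.* N reproduces, and it is adequate on its own terms under either form of baseline adjustment. Section 4.4 calls 40% conservative and does not tie it to T1. Section 6.6 recontacts dropouts "to supply the researchers with a post measurement and follow-up". With 25% loss, or with r = 0.6, even the free-baseline contrast reaches 80%.
- *Data-driven adjustment invalidates the test.* No inflation of type I error appeared. Stratifying on current versus remitted depression should also limit baseline IDS-C imbalance.

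**Conclusion.** The point holds as a gap between the sample size and the analysis text. Section 4.4 counts on baseline adjustment of the T1 comparison; sections 8 and 8.1 do not fix it, and 8.1 does not name T1 as the tested contrast.

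At r = 0.5, the difference between a fixed adjustment and a free-baseline change contrast is about 7 to 8 percentage points of power across 20-40% loss at T1. A fall below 80% needs three things together: the free-baseline reading, r of about 0.5 or less, and roughly 30-40% loss already at T1. Adjustment was the more powerful option in every case computed. This is a free improvement rather than an error in N.

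**What to change.** State in section 8.1 that:

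- the primary test is the MBCT + TAU minus TAU difference in IDS-C at T1, two-sided 0.05;
- it is estimated from the multilevel model with baseline IDS-C always adjusted for, regardless of observed imbalance, either as a covariate with the follow-up visits as outcomes or with baseline means constrained equal across arms;
- the T2-T5 contrasts are secondary.

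If an unconstrained change model is preferred, 4.4 should restate power as about 73% under r = 0.5 and 40% loss at T1.

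The cost is wording only. IDS-C is already collected at T0, and N, visits and burden are unchanged. Both forms of adjustment need T0 to come before randomisation, as the text of 6.3 says. The flowchart in Figure 2 lists randomisation first and should be brought into line. Whether 160 suffices once the random therapy-group effect is allowed for is a separate question.

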## 8.2 Secondary study parameter(s)

The secondary analysis is aimed at comparing the effects of MBCT + TAU on (hypo)manic and anxiety symptoms, quality of life, rumination, mindfulness and self-compassion skills. The secondary outcome parameters will be the total scores on the YMRS, FAST, STAI, RPA, MHC-SF, SCS-SF, CHIME, and the brooding subscale of the RRS. In order to investigate consolidation of treatment effect, we will follow-up participants for another 15 months. We will use a multilevel regression model for repeated measures to analyse differences between baseline, 3 months, 6 months, 9 months, 12 months, and 15 months follow-up measurements.

Furthermore, cost-effectiveness evaluation is carried out from a societal perspective considering direct as well as indirect costs. Data on resource use (health care uptake) and productivity losses will be collected with the Tic-P. Total costs for each patient will be obtained by multiplying these data with standard costs, based on the Dutch guideline for costing research (Hakkaart et al., 2002). Overall mean and median costs will be compared across the conditions and where relevant, differences will be calculated inclusive of 95% confidence intervals.

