is associated with goal-directed activity and decreased sleep, which intensifies symptoms of mood elevation (Gruber, 2011). According to Segal, Williams, and Teasdale (2002), training in mindfulness should decrease the tendency of depressed patients to enter a vicious cycle of negative ruminative thinking. Studies investigating reductions of negative rumination during MBCT are scarce (Michalak, Holz, & Teismann, 2010). In a sample of 55 treatment-resistant depressed patients, Eisendrath et al. (2008) found significant reductions of negative rumination following MBCT. The study of Deckersbach et al. (2012) found a significant decrease of negative rumination after MBCT in a sample of ten BD patients. Other studies found statistical trends towards reductions of negative ruminative thinking after MBCT in a sample of 19 patients with residual depressive symptoms (Kingston, Dooley, Bates, Lawlor, & Malone, 2007), and 95 BD patients (Perich et al., 2013). To our knowledge, no studies to date have investigated the effect of MBCT on ruminative responses to positive affect in BD patients. The present study will be the first to examine differences in ruminative responses to both positive and negative affect following MBCT in BD patients.

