#### Self-report measures

- *Quick Inventory of Depressive Symptomatology Self Report* (QIDS-SR; Rush et al., 2003). The QIDS-SR is a 16-item self-report version of the IDS-C. The QIDS-SR has good psychometric qualities.
- Altman self-rating mania scale (ASRM; Altman, Hedeker, Peterson, & Davis, 1997). The ASRM is a 5-item self-report questionnaire, with each item representing one of the major symptoms of mania, rated in increasing severity from 0 (not present) to 4 (present in severe degree). The ASRM has good psychometric properties.
- Prospective Life Chart, self-report, Dutch translation (Kupka, Akkerhuis, Nolen, & Honig, 1997). The Prospective Life Chart documents the course and severity of recurrent affective episodes. The current study will use the Life Chart prospectively in order to gain more fine-grained information about the severity of (hypo)manic or depressive symptoms over time, across the entire study period (15 months). The Life Chart has been shown a valid and reliable instrument to document the severity of affective episodes (Kupka et al., 1997).
- State/Trait Anxiety Inventory (STAI; Spielberger, 1983). The STAI is a self-report measure which has been proven reliable and sensitive in the assessment of both state and trait

levels of anxiety. It is a standard international measure in anxiety research and its Dutch translation has been shown valid (Van der Ploeg, 2000).

- Brooding subscale of the extended version of the Ruminative Response Scale (RRS-EXT; Treynor, Gonzalez, & Nolen-Hoeksema 2003). The authors reported adequate internal consistency (α = .79) and test–retest stability (α = .62, with a one year time interval) for the brooding subscale, which consists of five items. We select the brooding subscale because over time, brooding, or rumination, has been more strongly related to levels of depression (Treynor et al., 2003).
- The Comprehensive Inventory of Mindfulness Experience (CHIME; Bergomi, Tschacher, & Kupper, 2014). The CHIME is a 37-item, self-report questionnaire, divided in eight subscales measuring eight mindfulness aspects, including inner awareness, outer awareness, acting with awareness, acceptance, decentering, openness, relativity, and understanding. The CHIME has shown satisfactory to good change sensitivity, internal consistency, and test-retest reliability (Bergomi et al., 2014; Nila, Holt, Ditzen, & Aguilar-Raab, 2016).

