- Self-Compassion Scale short form (SCS-SF; Raes, Pommier, Neff, & Van Gucht, 2011). The present study will use the 12-item Dutch short-form version of the SCS-SF to measure self-compassion. The scale consists of six components, including self-kindness, selfjudgment, common humanity, isolation, mindfulness and over-identification. The SCS-SF has good reliability and validity (Raes et al., 2011).
- Mental Health Continuum short form (MHC-SF; Lamers, Westerhof, Bohlmeijer, ten Klooster, & Keyes, 2011). Lamers, 2011). The MHC-SF is a 14-item self-report questionnaire that assesses emotional, psychological and social well-being. It has adequate psychometric qualities in terms of good internal consistency, (moderate) testretest reliability, and good divergent and convergent validity.
- Responses to Positive Affect- Dutch Version (RPA-NL; Feldman, Joormann, & Johnson, 2008). The RPA is a 17-item questionnaire measuring self-reported levels of dampening and rumination in response to positive affect. The RPA-NL shows a satisfactory internal consistency (Raes, Daems, Feldman, Johnson, & van Gucht, 2009).
- *Childhood Trauma Questionnaire* (CTQ; Bernstein et al., 2003). This questionnaire with 28 intems assesses five domains of abuse and traumatic experiences during childhood (physical abuse, emotional abuse, sexual abuse, physical neglect and emotional neglect). The CTQ shows good criterion-related validity (Bernstein et al., 2003).
- *Treatment Credibility Questionnaire* (TCQ; Borkovec and Nau, 1972, adapted version by Addis et al. (2004), with one additional item from the Credibility Expectancy Questionnaire (Devilly and Borkovec, 2000). The TCQ that will be used in this study consists of 7 items that focus on credibility and expectancy of treatment. The TCQ shows good reliability (Borkovec & Nau, 1972).

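### Section 8.2 analyses the RPA only as a total, so no planned outcome isolates rumination on positive affect, which the Introduction says the trial will be the first to examine

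*Protocol*

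**What the plan says.** Protocol section 8.2 fixes the score: "The secondary outcome parameters will be the total scores on the YMRS, FAST, STAI, RPA, MHC-SF, SCS-SF, CHIME", and the sentence then adds the brooding subscale of the RRS. The aim given for this analysis includes "quality of life, rumination, mindfulness and self-compassion skills"; dampening is not named there.

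Protocol section 6.1.2, under the self-report measures, describes the instrument: "The RPA is a 17-item questionnaire measuring self-reported levels of dampening and rumination in response to positive affect". The protocol defines no RPA subscale outcome, no reverse scoring and no meaning for a higher or lower total.

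The Introduction (section 1) says that "no studies to date have investigated the effect of MBCT on ruminative responses to positive affect in BD patients" and continues: "The present study will be the first to examine differences in ruminative responses to both positive and negative affect following MBCT in BD patients".

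For negative rumination the protocol does choose a subscale and explains why: "We select the brooding subscale because over time, brooding, or rumination, has been more strongly related to levels of depression".

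**The concern.** Of the listed questionnaires, the RPA is the only one described as measuring rumination on positive affect. If it is analysed only as a total, the Introduction's question is addressed by a score that also contains something else. A treatment difference in the total could come from dampening alone, and a null total could hide a real change in rumination.

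At stake is the reading of one secondary result that the protocol presents as new. The protocol also expects benefit to be partly mediated by less ruminative thinking (section 2) and plans mediation analyses involving rumination (section 8.3). A score that mixes rumination with dampening would serve that purpose poorly too. If total and subscales are chosen between only after the data are seen, the choice is open to selection.

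**Working it through.** **Matching question to outcome**

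| Construct | Where it is raised | Planned score |
|---|---|---|
| Negative rumination | Section 1; section 2 (brooding) | RRS brooding subscale (8.2) |
| Positive rumination | Section 1 | RPA total, which includes dampening (8.2) |
| Dampening | Section 6.1.2 only, as part of what the RPA measures | RPA total (8.2) |

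Negative rumination has a score of its own. Positive rumination has none.

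**The plan's own figure**

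Inputs from section 4.4: two-sided alpha 0.05, power 80%, effect size 0.5, design factor 0.75, 40% loss to follow-up, 80 per group.

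- Per arm before adjustment: 2 × ((1.960 + 0.842) / 0.5)² = 62.8, rounded up to 63.
- With the design factor: 63 × 0.75 = 47.25, rounded up to 48.
- With 40% loss: 48 / 0.60 = 80 per arm, 160 in total.

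The stated N is reproduced. These inputs concern depressive symptoms. They are borrowed here only as a yardstick, because the protocol makes no power statement for the RPA.

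**What the total shows**

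Assumptions not in the documents: the two subscales have equal variance (SD 1 each), their correlation ρ lies between 0 and 0.5, and no items are reverse-scored. Let δR and δD be the treatment effects on rumination and dampening, in SD units. The total has SD √(2 + 2ρ), so

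d(total) = (δR + δD) / √(2 + 2ρ).

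Power is from a two-sided two-sample t-test with 48 completers per arm and standardised effect d / √0.75.

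| Scenario | d at ρ = 0 | d at ρ = 0.5 | Power |
|---|---|---|---|
| Rumination score alone, δR = 0.5 | 0.50 | 0.50 | 80% |
| Total, δR = 0.5, δD = 0 | 0.5/√2 = 0.354 | 0.5/√3 = 0.289 | 51% to 37% |
| Total, δR = 0.5, δD = −0.5 | 0 | 0 | no effect to detect |
| Total, δR = δD = 0.5 | 1.0/√2 = 0.707 | 1.0/√3 = 0.577 | 98% to 90% |

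**Wider assumptions**

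Suppose 6, 9 or 11 of the 17 items measure rumination, subscale SD is proportional to item count, and ρ runs from −0.2 to 0.5. With a normal approximation, the rumination score alone has power 0.81. For the total:

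- dampening unchanged: d = 0.20 to 0.48, power 0.21 to 0.78;
- dampening moving 0.5 SD the other way: d = −0.22 to 0.22, power 0.04 to 0.24, with the sign reversed when rumination has the fewer items;
- dampening falling by the same 0.5 SD: d = 0.57 to 0.79, so no dilution.

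The power consequence therefore ranges from severe loss to gain. The attribution problem is present in every row for the total, including the last.

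**The case against.** Four arguments weigh against the point.

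- **Opposed constructs.** A reader might infer that the total adds two opposed responses and so has no meaning. The documents do not support this. The Introduction links positive rumination to mood elevation, but the protocol does not say what dampening does, that the two are opposed, or how the items are keyed. If one set were reverse-scored, the total could be a coherent dimension. This part of the objection stands.
- **Objectives.** A reader might infer that a stated objective goes unanswered. Section 2 names only ruminative brooding among the secondary objectives, and brooding has its own score. Positive rumination is raised in the Introduction. That also stands, and it lowers the severity.
- **Power.** A reader might take 51% to 37% as the consequence. It holds only if dampening does not change. If both responses fall together, the total is more powerful than the subscale. This stands as well.
- **Level of detail.** The same sentence assigns totals to other multi-scale instruments, does not forbid subscale reporting, and scoring detail often belongs in an SAP. This carries less weight. The protocol does not leave the RPA score open: it names the total, and in the same sentence names a subscale for the RRS. An SAP that followed it would analyse the total.

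**Conclusion.** The point holds as a mismatch between question and outcome. The Introduction promises to examine rumination on positive affect, and the only RPA score fixed in section 8.2 cannot separate it from dampening. That follows from the protocol's own description of the instrument and needs no numerical assumption.

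The effect on power is conditional. Under equal subscale variances, correlation 0 to 0.5, 48 completers per arm and variance factor 0.75, power for a 0.5 SD effect on rumination goes from 80% on its own score to 51% to 37% on the total if dampening is unchanged. It vanishes if dampening moves equally in the opposite direction, and rises to 98% to 90% if both fall equally. The protocol gives no basis for preferring one of these. It would therefore be wrong to conclude that the total is meaningless, that power is necessarily lost, or that a formal objective is left without an outcome.

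The RPA is one secondary outcome. The primary analysis and N = 160 are unaffected. Severity is minor to moderate.

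**What to change.** In section 8.2, take the RPA out of the list of total scores. Name two scores instead: the RPA rumination score, as the outcome for the Introduction's question on positive affect, and the RPA dampening score, reported separately. State which items form each score and which direction counts as improvement, and make the change before outcome data are seen.

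The cost is one wording change and one more secondary outcome to report and interpret. All items are already collected at every assessment, so participant burden, sample size and the primary analysis do not change.
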